**18.2.3. SENSITIVITY ANALYSIS OF PRIMARY AND KEY SECONDARY EFFICACY VARIABLES**

**18.2.3.1. Completer Analysis**

The completer analysis set (CAS) will be used as a sensitivity analysis for all primary and key secondary efficacy endpoints. There will be no imputation for missing data.

[REDACTED]

Version Number: 1.7  
 Version Date: 21Mar2018

[REDACTED]

18.2.3.2. Adjunctive Lipid-modifying Therapy (LMT) Analysis

To explore the potential impact from adjunctive lipid-modifying therapy use during the study, a sensitivity analysis will be performed for primary and key secondary endpoints using data prior to the change of the post-baseline LMT only, i.e., lab test date  $\leq$  change date of LMT. There will be no imputation for missing data.

18.2.3.3. On-treatment Analysis

An on-treatment analysis will also be conducted for primary and key secondary endpoints using data collected from the on-treatment period, i.e. lab test date  $\leq$  of last dose of double-blind IMP+7 days. On-treatment analysis will be based on FAS. There will be no imputation for missing data.

18.2.3.4. Observed Data Analysis

The observed case data with no imputation for missing data will be used in sensitivity analyses for primary and key secondary endpoints.

**18.2.4. SUBGROUP ANALYSIS OF EFFICACY VARIABLE**

The primary endpoint for LDL-C will be analysed within subgroups below using the same analysis method previously described. The treatment and subgroup interaction will be examined by including the interaction term in the ANCOVA model for the overall population first. No imputation will be performed on missing data for subgroup analyses. In case the number of subjects within a subgroup is too small, e.g. less than 5% of the overall population, the analyses may not be performed or the subgroup levels may be combined. Forest plots for the primary efficacy variable will also be presented.

- CVD risk category (primary prevention; secondary prevention)
- Baseline LDL category (<130mg/dL,  $\geq$ 130 mg/dL and < 160 mg/dL,  $\geq$ 160mg/dL )
- History of diabetes (yes vs.no)
- Age (< 65 yrs. vs.  $\geq$ 65 yrs. and <75 yrs vs.  $\geq$ 75 yrs)
- Race (White vs. Non-White))
- Gender (male vs. female)
- BMI category (< 25 vs. 25 - < 30 vs.  $\geq$  30 kg/ m2)
- Background lipid modifying therapy (statin vs. non-statin vs. none)

[Redacted]

Version Number: 1.7  
 Version Date: 21Mar2018

[Redacted]

## 18.3. TERTIARY EFFICACY

### 18.3.1. TERTIARY EFFICACY VARIABLES & DERIVATIONS

[figure not shown]
The tertiary efficacy endpoints are:

[figure not shown]
### 18.3.2. MISSING DATA METHODS FOR TERTIARY EFFICACY VARIABLES

No missing data imputation will be performed for the tertiary endpoint analyses, only observed data will be used.

### 18.3.3. ANALYSIS OF TERTIARY EFFICACY VARIABLES

### 18.3.4. ADDITIONAL ANALYSIS

Version Number: 1.7  
Version Date: 21Mar2018

## 19. SAFETY OUTCOMES

All outputs for safety outcomes will be based on the Safety Analysis Set.

There will be no statistical comparisons between the treatment groups for safety data, unless otherwise specified with the relevant section.

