5.1.2. Secondary Objectives

- To evaluate the effect of 24-week treatment with bempedoic acid 180 mg/day versus placebo on LDL-C
- To evaluate the effect of bempedoic acid 180 mg/day versus placebo on non-high-density lipoprotein cholesterol (non-HDL-C), total cholesterol (TC), hs-CRP, and apolipoprotein B (apoB) after 12 weeks of treatment
- To evaluate the 24-week safety and tolerability of bempedoic acid 180 mg/day compared to placebo

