5.2.3. Tertiary Endpoints

5.2.4. Safety Endpoints

[figure not shown]
1. Patient incidence to TEAE
2. Safety laboratory values and vital signs
3. Cardiovascular event rates

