11.7. Safety Analysis

The summarization of AEs will include TEAEs, defined as any unfavorable and unintended sign, symptom, or disease temporally associated with the use of the investigational product, whether or not related to the product. TEAEs and SAEs will be summarized by SOC, severity, and relationship to study drug for each treatment group. These AE summaries will include cumulative incidence (percent of patients experiencing the AE) and patient-year adjusted incidence rates. If appropriate, absolute and relative risk differences will be calculated using both cumulative incidence and incidence rates. Deaths, withdrawal from study treatment due to AEs, and withdrawal from the study due to AEs will each be summarized by treatment group.

Clinical safety laboratories, including hematology, blood chemistry, coagulation, HbA_{1C}, glucose, and urinalysis; PE findings; vital signs; ECG readings; and weight will be summarized by the value and by change from baseline in the value (where appropriate) at each post baseline time point.

Hepatic Safety

For liver-associated enzymes and TB, the number and percent of patients with abnormal values for ALT, AST, and TB will be summarized. Hy's law criteria ($\geq 3 \times$ ULN for either ALT or AST, with accompanying TB $> 2 \times$ ULN (conjugated [direct] if Gilbert's Disease) in the absence

of other known causes) will also be applied to the data; any potential Hy's law cases will be listed separately.

Musculoskeletal Safety

AEs of muscle-related symptoms will be summarized by treatment group. In addition, the number and percent of patients with abnormal CK values will be summarized.

Diabetes/Glycemia

Cases of new onset of diabetes will be recorded as AEs and will be summarized using the appropriate SOC. These events will be summarized by severity and relationship to study drug for each treatment group.

Renal Safety

Baseline eGFR and values of CK will be summarized by treatment group and by baseline eGFR categories. Shift tables of eGFR category from baseline over the study, will be provided by treatment group. Finally, muscle-related AEs will be summarized by treatment group and by baseline eGFR category.

Neurocognitive Events

Neurocognitive events will be identified and evaluated by routine safety monitoring of PE findings and AEs. Summarization of neurocognitive events will occur using prespecified MedDRA terms and will be performed by treatment group.

Clinical endpoints

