**19.1.2. TEAEs LEADING TO DISCONTINUATION OF STUDY MEDICATION**

TEAEs leading to permanent discontinuation of study medication will be identified by using the response of 'Drug Withdrawn/Permanently discontinued' on the Action Taken with Study Drug Field on the AE eCRF page. For TEAEs leading to discontinuation of study medication, summaries of incidence rates (frequencies and percentages) by SOC and PT will be summarized.

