### 19.3. CLINICAL ENDPOINTS

Clinical endpoints will be monitored and adjudicated by an independent blinded expert CEC for this study. The following clinical endpoints will be tabulated:

- CV death (MACE)
- Nonfatal myocardial infarction [MI] (MACE)
- Nonfatal stroke (MACE)
- Hospitalization for unstable angina (MACE)
- Coronary revascularization (MACE)
- Non-coronary arterial revascularization (non-MACE)
- Hospitalization for heart failure (non-MACE)
- Non-CV death (non-MACE)

Additional details regarding clinical endpoints and clinical endpoint definitions will be included in CEC charter. The number of incidences and percentage of patients with each positively adjudicated outcome will be presented in a table. Only treatment emergent positively adjudicated events will be presented in the summary table. All adjudicated events will be included in a listing.

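### Protocol 11.7 calls for patient-year adjusted adverse event rates and, conditionally, risk differences; SAP 19 plans only percentages by arm and gives no reason

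*SAP*

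**What the plan says.** **Protocol.** The secondary objectives (5.1.2) include "To evaluate the 24-week safety and tolerability of bempedoic acid 180 mg/day compared to placebo". Section 11.7, on TEAEs and SAEs, says: "These AE summaries will include cumulative incidence (percent of patients experiencing the AE) and patient-year adjusted incidence rates". It continues: "If appropriate, absolute and relative risk differences will be calculated using both cumulative incidence and incidence rates". The synopsis repeats both sentences. The safety endpoints (5.2.4) include "Cardiovascular event rates", with no denominator specified. Section 11.1 gives the SAP precedence over the protocol on data analysis wherever the two differ.

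**SAP.** Section 2.2 keeps the safety objective unchanged. Section 19 begins: "There will be no statistical comparisons between the treatment groups for safety data, unless otherwise specified with the relevant section". No readable part of 19.1 to 19.8 specifies an exception. TEAEs are presented as incidence by SOC and PT (19.1.1). For TEAEs leading to discontinuation (19.1.2), "summaries of incidence rates (frequencies and percentages) by SOC and PT will be summarized". For adjudicated events (19.3), "The number of incidences and percentage of patients with each positively adjudicated outcome will be presented in a table". The readable safety text mentions no patient-years, risk differences or risk ratios, and does not explain their absence. Section 17.1 does derive treatment exposure from first to last dose, and section 19.1 limits TEAEs to a window ending 30 days after the last dose.

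**The concern.** Two things are lost if the SAP is followed as it reads.

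The first is comparability of the percentages. A patient who stops drug early has a shorter TEAE counting window, because it closes 30 days after the last dose. If one arm stops drug more often, its patients are at risk for less time. Its crude percentage then understates its event rate relative to the other arm. A patient-year rate deals with this.

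The second is precision. With one arm twice the size of the other and 300 patients in all, two percentages side by side do not show how large an excess of harm the data leave open. A similar percentage in each arm can be read as reassurance that the numbers do not support.

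**Working it through.** The plan states no adverse event rate, discontinuation rate or safety precision, so there is no figure of its own to reproduce. The check is first textual and then illustrative.

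**Protocol and SAP side by side**

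| Item | Protocol | Readable SAP |
|---|---|---|
| Patient-year adjusted AE rates | Unconditional (11.7, synopsis) | Not mentioned; 19.1.2 uses the term incidence rates for counts and percentages |
| Risk differences for AEs | Conditional on being appropriate | Not mentioned; statistical comparisons ruled out in 19 |
| Adjudicated clinical endpoints | Summarized by event type and arm (11.7) | Counts and percentages (19.3) |
| Objective compared with placebo | Yes (5.1.2) | Yes (2.2) |

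The first two rows are departures. The third is not: the patient-year sentence in 11.7 concerns AE summaries, and 19.3 delivers what 11.7 asks for adjudicated endpoints.

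**Time at risk (assumed discontinuation)**

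Inputs from the documents: 24 weeks = 168 days of treatment, plus the 30-day window. Assumptions: a fraction d of an arm stops drug, at Day 60 on average, and the event rate is constant.

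Mean time at risk = (1 − d) × (168 + 30) + d × (60 + 30) = 198(1 − d) + 90d.

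- 18% v 9% stopping: 0.82 × 198 + 0.18 × 90 = 178.6 days; 0.91 × 198 + 0.09 × 90 = 188.3 days; ratio 0.948.
- 15% v 10%: 181.8 / 187.2 = 0.971.
- 20% v 10%: 176.4 / 187.2 = 0.942.
- Equal d in both arms: ratio 1, so no bias.

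Under these splits the crude percentage understates the rate in the arm that stops more by about 3-6% relative. The approximation is best for uncommon events.

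**Precision of a risk difference**

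Inputs: 200 and 100 patients (2:1 split of 300; SAP 3.1) and a 95% interval (SAP 6.5). A common event rate p is assumed.

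Half-width = 1.96 × √[p(1 − p)(1/200 + 1/100)].

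| p | Half-width (percentage points) |
|---|---|
| 2% | 3.4 |
| 5% | 5.2 |
| 10% | 7.2 |
| 20% | 9.6 |

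As an example, assumed counts of 30/200 (15%) and 10/100 (10%) give a difference of 5.0 points, with a 95% Newcombe interval of −3.6 to 12.2.

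**The two compared.** A 5% relative bias is about 0.5 points at a 10% event rate (half-width 7.2) and about 1 point at 20% (half-width 9.6). The precision left unstated is much larger than the likely bias.

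**The case against.** The sponsor has a fair reply on several counts.

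- **Omission is not withdrawal.** The SAP prevails only where the documents differ, so the sponsor could say that the patient-year rates survive its silence. A rate within one arm is not a between-arm comparison, so the opening sentence of SAP 19 does not bar it. This stands as a limit on wording. It does not remove the gap: the SAP is meant to give the specifics, and its one gloss on incidence rates, confined to 19.1.2, points to percentages.
- **Risk differences were conditional.** The SAP may be using that discretion. This stands, but nowhere does the SAP say that they were judged inappropriate.
- **Ruling out statistical comparisons may mean only no hypothesis tests.** That is plausible. Even so, no section supplies a difference, ratio or interval.
- **Templates.** SAP 8 and 19.1 defer table content to templates that are not in the documents and may contain more. A reader might infer that the rates will certainly not be produced; the documents do not support that.
- **Little information is lost.** With arm counts and denominators, a reader can compute a crude risk difference and its interval. This stands for crude differences. Exact event-specific person-time cannot be recovered from such tables.
- **The size of the bias is assumed.** The documents give neither the discontinuation split nor its direction. A patient who stops because of a TEAE is already counted for that event, so the lost time does not understate it.

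A reader might also infer that SAP 19.3 breaks a commitment on cardiovascular events. It does not, because 11.7 attaches no patient-year requirement to adjudicated endpoints and 5.2.4 names no denominator.

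**Conclusion.** The concern holds in a limited form. One unconditional protocol analysis, the patient-year adjusted AE rates, is missing from the readable SAP. One conditional analysis, the risk differences, is missing without a stated judgement that it was inappropriate. The SAP still claims the objective of safety compared with placebo. By-arm percentages allow a descriptive comparison, so it would be too strong to say that the objective goes unaddressed. What is absent is a planned comparative estimate with its uncertainty.

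The possible bias is small and rests on assumptions. The precision figures rest only on the planned arm sizes and an assumed common event rate. This should be corrected; it does not threaten the trial's efficacy conclusions.

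**What to change.** In SAP 19.1:

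1. Add patient-year adjusted rates for TEAEs and serious TEAEs. Define patient-time as first dose to the end of the window of last dose plus 30 days, censored at the first event where a first-event rate is reported.
2. For the main summary rows (any TEAE, serious TEAE, TEAE leading to discontinuation, each AESI category), add a risk difference with 95% CI by a named method, for example Miettinen-Nurminen. Give no p-values.
3. Reword the opening sentence of SAP 19 so that it rules out hypothesis tests rather than all comparisons.

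If the sponsor prefers not to add these, the SAP should state and justify the departure and be reconciled with Protocol 11.7. Patient-year rates for adjudicated events in 19.3 would be an optional addition serving the cardiovascular event rate endpoint.

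The cost is SAP wording and extra columns in existing tables. No new data are needed, because the SAP already derives exposure and defines the counting window, and there is no effect on alpha. The drawback is a set of many unadjusted intervals, which should be labelled descriptive. The December 2018 addendum says that the planned analyses are complete. The patient-year rates could still be reported as specified in the protocol, but an interval method chosen now should be identified as chosen after unblinding.

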### 19.1. ADVERSE EVENTS

Adverse Events (AEs) will be coded using MedDRA, Version 20.1.

Treatment emergent adverse events (TEAEs) are defined as AEs that started or worsened in severity after the first dose of IMP (double-blind study medication) and prior to the last dose date of double-blind study medication + 30 days. AEs that occurred on day 1 will be only be determined as TEAE if the site indicated it occurred after first dose on the AE CRF.

See [Appendix 2](#) for handling of partial dates for AEs. In the case where it is not possible to define an AE as treatment emergent or not, the AE will be classified by the worst case, i.e. treatment emergent.

An overall summary of number of subjects within each of the categories described in the subsection below, will be provided as specified in the templates. Listings will include TEAEs and Non-TEAEs.

#### 19.1.1. ALL TEAEs

Incidence of TEAEs will be presented by System Organ Class (SOC) and Preferred Term (PT) and also broken down further by maximum severity and relationship to study medication. Adverse events by the subgroups in [Section 18.2.4](#) with the exception of baseline LDL subgroup will also be presented.

##### 19.1.1.1. Severity

Severity is classed as mild/ moderate/ severe (increasing severity). TEAEs starting after the first dose of IMP with a missing severity will be classified as severe. If a patient reports a TEAE more than once within that SOC/ PT, the AE with the worst case severity will be used in the corresponding severity summaries.

##### 19.1.1.2. Relationship to Study Medication

Relationship to IMP, as indicated by the Investigator, is “not related” if the TEAE is “not related” or “unlikely”. A “related” TEAE is defined as a TEAE with a relationship of “possibly related”, “probably related”, or “definitely related” to study medication. TEAEs with a missing relationship

Version Number: 1.7  
 Version Date: 21Mar2018

to study medication will be regarded as "probably related" to study medication. If a patient reports the same AE more than once within that SOC/ PT, the AE with the worst case relationship to study medication will be used in the corresponding relationship summaries.

**19.1.2. TEAEs LEADING TO DISCONTINUATION OF STUDY MEDICATION**

TEAEs leading to permanent discontinuation of study medication will be identified by using the response of 'Drug Withdrawn/Permanently discontinued' on the Action Taken with Study Drug Field on the AE eCRF page. For TEAEs leading to discontinuation of study medication, summaries of incidence rates (frequencies and percentages) by SOC and PT will be summarized.

**19.1.3. SERIOUS ADVERSE EVENTS**

Serious adverse events (SAEs) are those events recorded as 'serious' on the adverse events page of the eCRF. Summaries of serious TEAEs and serious related TEAEs by SOC and PT will be prepared.

**19.1.4. ADVERSE EVENTS OF SPECIAL INTEREST (AESI)**

Adverse events of special interest will be identified by pre-specified MedDRA preferred terms provided by Esperion Therapeutics Inc. (see [Appendix 5](#)). These events will be summarized by AESI category, SOC and PT. All AESI will be summarized by severity and relationship to study medication. In addition, AESI will be evaluated by monitoring safety labs as detailed in [section 19.4](#).

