10.2.11. Adverse Events of Special Interest (AESI)

10.2.11.1. Potential Adverse Events Based on Findings in Bempedoic Acid Clinical Studies

Across clinical studies to date, the most frequently reported TEAEs included musculoskeletal and connective tissue disorders (back pain, pain in extremity, myalgia, arthralgia, and muscle spasms), nervous system disorders (headache), gastrointestinal (GI) disorders (nausea and diarrhea), and infections and infestations. Overall, AEs were generally reported with similar incidence between those patients treated with bempedoic acid, bempedoic acid in combination with ezetimibe or statin therapy, ezetimibe, statins, or placebo; however, the incidence of headache was higher with bempedoic acid than placebo.

In general, laboratory results showed no clinically significant trends at the data cut-off for End-of Phase 2. A total of 7 patients receiving bempedoic acid monotherapy or in combination with a statin or ezetimibe experienced repeated and confirmed ALT and/or AST $>3 \times$ the ULN; in 1 of these patients receiving bempedoic acid 80 mg the elevation was assessed by Investigator as not related to study drug because the patient tested positive for acute cytomegalovirus (CMV) infection. One patient receiving ezetimibe monotherapy experienced repeated and confirmed ALT and/or AST $>3 \times$ ULN. All liver function test (LFT) abnormalities were considered mild to moderate and improved upon removal of the study drug. Small group mean increases in uric acid and homocysteine, and decreases in hemoglobin have been observed, but in general, these shifts have not been associated with clinical symptoms. Changes in vital signs, ECG, PE, and other physical findings presented no safety issues in any of the clinical studies.

Monitoring and Management of Elevated Serum Creatinine

If at any time after randomization, a patient experiences a decrease in eGFR to the level of 15 mL/min/1.73 m²) or if the patient experiences acute renal failure, the patient should be withdrawn from IMP treatment but will be asked to continue to be followed for safety using the protocol-specified visit schedule (see [Section 8.3](#)).

Monitoring and Management of Hemoglobin Change

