If at any time after randomization a patient experiences a decrease >2.0 g/dL (20 g/L) from baseline (Week 0 [Visit T1]), the patient will undergo repeat confirmatory hematology testing as soon as is reasonably possible, preferably within 3 to 7 days of the laboratory result becoming available.

[figure not shown]
Repeat hematology assessment will include: 1) measurement of Hgb, hematocrit (Hct), mean corpuscular hemoglobin, mean corpuscular hemoglobin concentration, mean corpuscular volume, platelet count, reticulocyte count (percent and absolute), red blood cell count (RBC), and white blood cell count (WBC) with differential (absolute values only); 2) history of concomitant medication use; and 3) query for related symptoms. Additionally, further testing

may be warranted to rule out additional pathology depending on clinical presentation, and should be discussed with Esperion Therapeutics personnel or the authorized Medical Monitor.

- If repeat Hgb assessment confirms a decrease >2.0 g/dL (20 g/L) from baseline, the patient should be monitored carefully during the study and return at 2 week intervals after study completion for additional Hgb measurement until the level returns to baseline or reaches a stable level.
- If repeat Hgb assessment confirms Hgb <8 g/dL (80 g/L), the patient should be withdrawn from treatment with study drug. The patient will return at 1-week intervals after withdrawing from study drug treatment for additional Hgb measurement until the level returns to baseline or reaches a satisfactory conclusion.
- If the patient is withdrawn from study drug treatment, the patient should be asked to continue being followed for safety using the protocol-specified visit schedule (see [Section 8.3](#)).

At any time, the investigator may choose to consult with a specialist to further evaluate the cause of the alteration in hemoglobin.

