### APPENDIX 3. LIST OF DMC TABLES, LISTINGS AND FIGURES

#### TABLES

- 14.1.1.1 Patient Disposition – All Patients
- 14.1.2.1a Demographic and Other Baseline Characteristics – Full Analysis Set
- 14.1.3.1 Medical/Surgical History – Full Analysis Set
- 14.1.3.3 Targeted Cardiovascular History/Risk Factors – Full Analysis Set
- 14.1.5.1 Study Drug Compliance – Safety Analysis Set
- 14.3.1.1 Overview of Treatment-Emergent Adverse Events – Safety Analysis Set
- 14.3.1.2 Treatment-Emergent Adverse Events by Maximum Severity, System Organ Class and Preferred Term – Safety Analysis Set
- 14.3.1.3 Serious Treatment-Emergent Adverse Events by Maximum Severity, System Organ Class and Preferred Term – Safety Analysis Set
- 14.3.1.4 Related Treatment-Emergent Adverse Events by Maximum Severity, System Organ Class and Preferred Term – Safety Analysis Set
- 14.3.1.5 Related Serious Treatment-Emergent Adverse Events by Maximum Severity, System Organ Class and Preferred Term – Safety Analysis Set
- 14.3.1.6 Treatment-Emergent Adverse Events That Led to Discontinuation of Study Drug by Maximum Severity, System Organ Class and Preferred Term – Safety Analysis Set
- 14.3.1.8 Treatment-Emergent AESIs by Maximum Severity, System Organ Class and Preferred Term – Safety Analysis Set
- 14.3.1.15 Investigator-reported Major Cardiac Events (MACE) by Event Type – Safety Analysis Set
- 14.3.1.16 Adjudicated Major Cardiac Events (MACE) by Event Type – Safety Analysis Set
- 14.3.2.8 Laboratory Parameters of Interest: Observed and Change from Baseline – Safety Analysis Set
- 14.3.2.9 Laboratory Parameters of Interest: Laboratory Abnormalities – Safety Analysis Set

Version Number: 1.7  
 Version Date: 21Mar2018

14.3.2.10 Quantitative Clinical Laboratory Evaluations: Lipids – Safety Analysis Set (note that this table is produced for DMC only)

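### The SAP's AESI term list has no haemoglobin/anaemia group and counts gout as a renal disorder, so anaemia-type events get no pooled AESI count and the renal total can include gout

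*SAP*

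**What the plan says.** SAP 19.1.4 defines AESIs through a term list: "Adverse events of special interest will be identified by pre-specified MedDRA preferred terms provided by Esperion Therapeutics Inc", with Appendix 5 as the list. On reporting it says "These events will be summarized by AESI category, SOC and PT", and it promises severity and relationship summaries for all AESIs. It also adds a second route: "In addition, AESI will be evaluated by monitoring safety labs as detailed in" section 19.4. The term list feeds one of the DMC outputs in Appendix 3, "14.3.1.8 Treatment-Emergent AESIs by Maximum Severity, System Organ Class and Preferred Term".

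Protocol 10.2.11 is the AESI section. Its subsection 10.2.11.1 says of earlier bempedoic acid studies: "Small group mean increases in uric acid and homocysteine, and decreases in hemoglobin have been observed". Under the subheading "Monitoring and Management of Hemoglobin Change" it sets a procedure that starts "If at any time after randomization a patient experiences a decrease >2.0 g/dL (20 g/L) from baseline (Week 0 [Visit T1" and goes on to repeat testing, follow-up, and a confirmed level below 8 g/dL at which study drug is withdrawn.

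Appendix 5 labels its category column as following the protocol. The eight categories are creatine kinase elevations, new or worsening diabetes, hepatic, hypoglycemia, metabolic acidosis, muscular, neurocognitive/neurologic and renal. Gout is listed in the renal category.

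**The concern.** A fall in haemoglobin is one of the few effects that the protocol's AESI section reports as already seen in patients on this drug. One would expect the adverse events that correspond to it to be grouped and counted as the other AESI topics are. If anaemia-type events are coded to several preferred terms, they appear as separate small lines. The number of patients with any such event cannot be obtained by adding those lines, because one patient may appear on more than one.

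The gout placement raises a different problem of interpretation. Uric acid increases were also seen in earlier studies. If gout occurred more often on bempedoic acid, the excess would add to the renal disorders total, and no uric-acid grouping would show it for what it is.

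**Working it through.** No figure in the plan is at issue, so the check sets the two documents side by side. The counts are rows in Appendix 5; the last column is the list of laboratory abnormalities of interest in SAP 19.4.

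| Topic | Appendix 5 rows | SAP 19.4 rows of interest |
|---|---|---|
| Creatine kinase / muscle | 4 + 14 | CK >5× and >10× ULN |
| Diabetes | 16 | fasting glucose ≥126 mg/dL, HbA1c ≥6.5% |
| Hepatic | 13 | ALT or AST >3× and >5× ULN, bilirubin >2× ULN |
| Hypoglycemia | 7 | fasting glucose ≤50 mg/dL |
| Metabolic acidosis | 1 | none |
| Neurocognitive | 6 | none |
| Renal | 17, one of them Gout | creatinine rise >1 mg/dL, eGFR <15 and 15 to <30 |
| Haemoglobin / anaemia | 0 | fall ≥2 g/dL, level <8 g/dL |
| Uric acid | 0 | none |

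The rows add to 4 + 14 + 16 + 13 + 7 + 1 + 6 + 17 = 78. The only row containing the word haemoglobin is glycosylated haemoglobin increased, which belongs to diabetes.

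**Haemoglobin.** For muscle, diabetes, liver and kidney the SAP uses both routes, coded terms and laboratory rows. For haemoglobin it uses laboratory rows only and gives no reason. The two routes do not capture the same thing:

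- SAP 19.4 takes central-laboratory results, so anaemia diagnosed elsewhere would not appear in those rows.
- Laboratory rows carry no investigator severity or relationship.
- Under protocol 10.1.6.4, an abnormal value not already tied to an AE becomes one when it leads to action on study drug, needs intervention, or is judged clinically significant. Those are the cases for which a grouped AE count is most useful.

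Hypoglycemia and metabolic acidosis, which the synopsis bases on nonclinical findings, do have term categories.

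**Gout.** Protocol 10.2.11.3.5 (Renal) deals with creatinine, eGFR and acute renal failure and does not mention gout. Neither document explains why gout is a renal term.

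The documents give no gout or renal AE rate, so what follows is illustration only. Let *g* be the share of patients with gout and *r* the share with any other renal term, assumed independent, in the planned 200 bempedoic acid patients. The share in the renal category is 1 − (1 − *g*)(1 − *r*), and gout adds 200 × *g* × (1 − *r*) patients.

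| *g* | *r* | Renal category share | Patients without gout → with gout | Added |
|---|---|---|---|---|
| 0 | 0.03 | 0.0300 | 6.0 → 6.0 | 0 |
| 0.01 | 0.03 | 1 − 0.99 × 0.97 = 0.0397 | 6.0 → 7.9 | 1.9 |
| 0.03 | 0.01 | 1 − 0.97 × 0.99 = 0.0397 | 2.0 → 7.9 | 5.9 |
| 0.03 | 0.05 | 1 − 0.97 × 0.95 = 0.0785 | 10.0 → 15.7 | 5.7 |

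**Other entries to verify.** Aspartate aminotransferase abnormal is listed twice and the matching increased term never, although ALT has both. Blood glucose abnormal sits under both diabetes and hypoglycemia. Myoglinuria, in the muscular list, looks misspelt beside Myoglobinaemia.

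**The case against.** The strongest reply is that haemoglobin is not missing. SAP 19.1.4 itself sends AESIs to the laboratory summaries, and SAP 19.4 tabulates both protocol levels (apart from >2.0 g/dL in the protocol against ≥2 g/dL in the SAP, which should be reconciled). The protocol procedure is triggered by laboratory values, so a laboratory table is a natural output for it. Every treatment-emergent event is also shown by preferred term, with severity and relationship, under SAP 19.1.1. The DMC receives all TEAEs (Table 14.3.1.2), related TEAEs (14.3.1.4), laboratory parameters of interest and their abnormalities (14.3.2.8 and 14.3.2.9), and haematology and chemistry boxplots. All of this stands. A reader might infer that an AESI goes unreported or that the DMC would not see anaemia; the documents do not support either.

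The synopsis section on potential AEs and AESIs also names neither haemoglobin nor uric acid, and the Appendix 5 categories match it, with clinical endpoints left to adjudication. Protocol 11.7 plans no haemoglobin AE summary. Inclusion in 10.2.11 does not by itself require a term group. So the SAP does not break an explicit promise, but it leaves the synopsis and the body of the protocol giving different pictures of what is of special interest.

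On gout, a reader might infer that the renal category is inflated or that a uric-acid signal is hidden. Neither is established. AESIs are shown down to preferred term, so gout keeps its own line, and with no gout events nothing changes. Nor does the protocol keep uric acid wholly apart from renal function: 10.2.11.1 contains both the uric acid remark and the serum creatinine rule. The visible text sets no procedure for uric acid, and 10.2.11.2 is blank in the public copy, so a rationale may exist that cannot be seen.

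The apparent misspelling may come from the PDF reading. Whether it would cause a missed match depends on the programmed look-up, which is not in the documents.

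**Conclusion.** The point holds in limited form. Followed as written, the plan gives no pooled AESI count, with severity and relationship, for anaemia-type adverse events, although the protocol's AESI section reports and monitors haemoglobin falls. It also gives a renal total that includes any patient whose only qualifying term is gout.

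The haemoglobin gap follows directly from the list: 0 of 78 rows. What is lost is a grouping, since the individual events are still reported. The effect of gout cannot be sized from the documents. The range of 0 to about 6 patients in 200 rests on assumed rates and independence, and it concerns only the category total. SAP 19 plans no between-group tests of safety data unless otherwise specified, so no error rate is shown to be affected, and the efficacy analyses are untouched. The change is worth making because it is cheap and makes two already observed drug effects easier to read. It does not call the trial's conclusions into question.

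**What to change.** In Appendix 5:

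- Add a haemoglobin decrease/anaemia group (for example anaemia, haemoglobin decreased, haematocrit decreased, red blood cell count decreased).
- Move Gout to a uric acid/gout group with the uric-acid-increase terms, or keep it where it is and show the renal total with and without gout.
- Check every listed term against MedDRA 20.1, the version the SAP names, including the duplicate AST row, the absent AST increased term, the shared glucose term and the spelling of Myoglinuria in the source file.

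With both new groups the list goes from 8 to 10 categories, and the renal group from 17 terms to 16.

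The cost is a small look-up edit and a rerun of the AESI tables. The SAP addendum of December 2018 says that the planned analyses were complete and that its additions followed unblinding. It adds a liver function table but none for haemoglobin or gout. A regrouping made after that point has to be labelled post hoc and shown beside the tables from the original list.
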